5.3. Baseline Definitions

For all efficacy analyses and the data tabulation of baseline disease characteristics, baseline is defined as the last value measured on or before the day of the first dose of IP. For the summaries of laboratory parameters, vital signs, and weight, baseline is defined as the last value measured on or before the day of the first dose of IP in the summaries for the placebo-controlled period, and defined as the last value measured on or before the start day (defined in Section 5.2) of the apremilast-exposure period in the summaries for the apremilast-exposure period.

5.4. Time points

Assessments will be done at the intervals specified in the Table of Events, Section 5 in protocol. During the trial, assessments can occur outside protocol specified intervals (i.e., Early Termination Visit or unscheduled visits). For the purpose of data analysis and reporting, all assessments will be assigned to analysis visits according to a visit window schema (See [Table 2](#) and [Table 3](#)), which is defined as the study day ranges relative to either the date of first dose of IP or apremilast 30 mg for placebo subjects who switch to the APR 30 BID group at Week 12.

If more than one assessment of a particular efficacy or safety variable occurs in the same study visit window (due to unscheduled visits or Early Termination visit), the assessment within given visit window that is closest to the target Study Day will be used for the analysis; in the case of ties, the later assessment will be used.

Table 2: Definition of Visit Window for Study Visit

| Visit Number | Week | Analysis Time Point | Target Study Day | Start (Study Day) | End (Study Day) |
|--------------|---------|---------------------|------------------|------------------------------------|--|
| Visit 2 | Week 0 | Baseline | 1 | | 1 |
| Visit 3 | Week 1 | Week 1 | 8 | 2 | 11 |
| Visit 4 | Week 2 | Week 2 | 15 | 12 | 22 |
| Visit 5 | Week 4 | Week 4 | 29 | 23 | 36 |
| Visit 6 | Week 6 | Week 6 | 43 | 37 | 50 |
| Visit 7 | Week 8 | Week 8 | 57 | 51 | 64 |
| Visit 8 | Week 10 | Week 10 | 71 | 65 | 78 |
| Visit 9 | Week 12 | Week 12 | 85 | 79 | 
 1) Last measure on or prior to first APR dose date on Visit 9 or 2) 1 day prior to date of Follow-up Visit if subjects discontinue study prior to Visit 9 and complete Follow-up visits or 3) ET visit if performed or date of treatment discontinuation if subjects discontinue study and have no Observational Follow-up Visits, whichever is later. |
| Visit 10 | Week 16 | Week 16 | 113 | First APR dose date on Visit 9 + 1 | 155 |
| Visit 11 | Week 28 | Week 28 | 197 | 156 | 239 |
| Visit 12 | Week 40 | Week 40 | 281 | 240 | 323 |
| Visit 13 | Week 52 | Week 52 | 365 | 324 | 407 |

| Visit Number | Week | Analysis Time Point | Target Study Day | Start (Study Day) | End (Study Day) |
|--------------|---------|---------------------|------------------|-------------------|---|
| Visit 14 | Week 64 | Week 64 | 449 | 408 | 
For subjects entering Active Treatment Phase but not entering optional Open-label Extension Phase:
 
 1) 1 day prior to date of Observational Follow-up Visit if Observational Follow-up Visit performed or 2) ET visit if performed or 3) Date of APR treatment discontinuation if subjects discontinue study and have no Observational Follow-up visits, whichever is later. 
For subjects from German sites entering the optional Open-label Extension Phase, the end day is when the IP is administered at Visit 14
 |

APR = Apremilast; ET = Early termination.

The time points for analyses of efficacy data will be assigned according to visit window scheme in [Table 2](#) which are set up as the continuous and mutually exclusive, from midpoint to midpoint between each successive part of scheduled visits or otherwise specified.

The time points for summaries of safety data (laboratory parameters, vital signs, and weight) will be assigned as defined above for both placebo-controlled and apremilast-exposure period for subjects who are randomized as APR30 BID; and for placebo-control period only (through Week 12) for placebo subjects. For all placebo subjects who switch to the APR 30 BID group at Week 12, safety data within apremilast-exposure period will be mapped to reflect the Study Days relative to the first dose of apremilast (see [Table 3](#) below). In addition, safety analysis on the end of treatment will be included, which is defined as the last visit among all the scheduled and unscheduled visits and, if applicable, the Early Termination visit, all within the same analysis period. The baseline visit and the Observational Follow-up Visit are not included in the derivation of the end-of-treatment value.

Table 3: Mapping of Study Weeks for Placebo Subjects who Switched Treatment in Summary of Safety Data over Time

| Visit | Week | Mapped Analysis Time Point | Target APR Day | Start (APR Day) | End (APR Day) |
|----------|---------|----------------------------|----------------|-----------------|--|
| Visit 9 | Week 12 | Baseline | 1 | | Last measure prior to First APR Dose Date(\leq 1 APR day) |
| Visit 10 | Week 16 | Week 4 | 29 | 2 | 71 |
| Visit 11 | Week 28 | Week 16 | 113 | 72 | 155 |
| Visit 12 | Week 40 | Week 28 | 197 | 156 | 239 |
| Visit 13 | Week 52 | Week 40 | 281 | 240 | 323 |
| Visit 14 | Week 64 | Week 52 | 365 | 324 | 407 |

Note: APR Day is the study day relative to the first apremilast dose date on Visit 9.

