## **6.10. Early Termination Visit**

The Early Termination Visit is based on the subject's withdrawal from any time during the study. In addition, the investigator may discontinue the subject from the study at any time based on his/her assessment of clinical efficacy and/or safety. The decision to discontinue a subject remains the responsibility of the treating physician, which will not be delayed or refused by the sponsor.

When a subject withdraws or is discontinued from the study, every effort should be made to complete as many safety and efficacy assessments as reasonably appropriate. Please see the Table of Events, [Section 5](#), for the assessments to be performed at the Early Termination Visit. The Observational Follow-up Visit (see [Section 6.11](#)) should also be scheduled 4 weeks ( $\pm 7$  days) after the subject's last dose of IP, regardless of the reason for IP discontinuation.

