4.2.5. Derivations of Efficacy Endpoints

Efficacy assessments, as detailed in the following section, will be done at the intervals specified in the Table of Events, Table 1 in the protocol.

- The number of oral ulcers and genital ulcers will be counted at each study visit, at ET and Observational Follow-up visits following the Placebo-controlled or Active Treatment Phase. For females, both vulvar and vaginal ulcers will be considered for genital ulcers.
- The AUC from baseline to Week 12/Day 85 (AUC_{85}) is the sum of the AUCs in each time interval specified by the dates of the visits. The individual AUC for any given time interval is calculated based on the linear trapezoidal method, which uses linear interpolation between data points to calculate the AUC. The AUC_{85} can be calculated as follows:

$$AUC = p * \sum_{k=2}^8 \frac{1}{2} (C_k + C_{k+1})(t_{k+1} - t_k), \quad k = 2, 3, \dots, 8,$$

and

$$p = \frac{(85-1)}{(t_9-t_2)} = \frac{84}{(t_9-t_2)} p = \frac{(85-1)}{(t_9-t_2)} = \frac{84}{(t_9-t_2)}.$$

where C_2, C_3, \dots, C_9 are the number of ulcers at each visit from Visit 2/Baseline to Visit 9/Week 12, and t_2, t_3, \dots, t_9 are the ulcer assessment dates for Visit 2/Baseline to Visit 9/Week 12. When Visit 9/Week 12 does not exactly coincide with Day 85, the AUC through Week 12 will be adjusted for the actual study duration by dividing the total AUC by total study duration (in days) and multiplying this quantity by 84 days.

- The multiple imputation method will be used to impute missing oral ulcer counts when deriving the primary efficacy endpoint of AUC for the number of oral ulcers.

- AUC using a last observation carried forward (LOCF) approach to impute missing assessments at Week 12 will be used as a sensitivity analysis. If a subject has no post baseline ulcer assessment excluding the value obtained at the Observational Follow-up Visit, the baseline value will be carried forward for calculation. If there is a missing oral ulcer assessment between two visits or time points with assessments within a period, the AUC will be calculated based on the preceding and subsequent ulcers count.
- The LOCF approach will also be used for all other efficacy endpoints based on oral or genital ulcers count including calculating the cumulative number of oral ulcers per subject at all scheduled visits from baseline to Week 12. Of note, the cumulative count does not distinguish new occurrence of ulcers or the same ulcers appeared previously.

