4.3. Stratification, Randomization, and Blinding

At Visit 2, subjects who meet entry criteria will be randomized using a permuted block randomization in parallel 1:1 (102 subjects per group) to receive either APR 30 BID or identically-appearing placebo BID for the 12-week Placebo-controlled Treatment Phase, using a centralized Interactive Response Technology (IRT). Eligible subjects will be stratified according to sex, history of uveitis, and region (Japan and Other).

This study will be conducted as a double-blind study for the Placebo-controlled Treatment Phase. During the Active Treatment Phase (Weeks 12 to 64), the IP will remain blinded, to prevent study personnel and subjects from knowing the IP assignment in the Placebo-controlled Phase.

To maintain the blind regarding the initial treatment assignment, all subjects will receive dose titration cards at Visit 9. Although only subjects initially randomized to placebo will be dose titrated during their first week of the Active Treatment Phase, all subjects entering the Active Treatment Phase will receive identically-appearing titration/treatment cards.

Data analyses and reporting will be performed after all subjects have completed Week 12/Visit 9 or have discontinued early (the 12-week database). After medical/scientific review has been completed, protocol violations/deviations have been identified, and the data have been declared final and complete, the 12-week database will be extracted and restricted with the corresponding external data files in the appropriate location in the data repository. For 12-week database lock, Celgene personnel who have access to the unblinded data are not to discuss or make materials available that would unblind individual subjects data to the personnel involved in the study conduct. Blinding to treatment assignment will be maintained at all study sites prior to the Week 68 database lock.

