4.4. Sample Size Determination

The sample size estimation is based on the consideration from the results of the Phase 2 study CC-10004-BCT-001. A 2-sided t-test at a 0.05 significance level will have 90% power to detect a treatment difference of 66 in the AUC of oral ulcer counts from Day 1 through Week 12 (AUC₈₅ of placebo – drug = 66), the primary efficacy endpoint, when the sample size in each group is 102, assuming a common standard deviation of 144.

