The number of oral ulcers following subject's first loss of a complete response will be summarized for subjects who have a complete response prior to Week 12. The number of oral ulcers will be summarized as zero for subjects who had no reappearance of oral ulcers following a complete response prior to Week 12. The comparison between two treatment groups will be performed using ANCOVA model with the treatment, sex and region as factors and baseline number of oral ulcers as a covariate. Within-group LS means, the associated SEs, and treatment differences in LS means, the associated SE, and associated 2-sided 95% CIs and 2-sided p-values will be derived from the model. The treatment comparison will only be conducted if appropriate.

The summary tables with descriptive statistics for number of oral ulcers and general ulcers will be presented by treatment group at all applicable analysis visits.

Summary tables for change from baseline with descriptive statistics will be presented for continuous variables including pain VAS of oral ulcers, pain VAS of genital ulcers, BD Current Activity Form Scores, BD QoL scores, BSAS scores,

, and total score of the Static PGA of skin lesions by treatment group at all applicable visits per study period. For the PGA, only subjects who had BD skin lesions at baseline will be included. For the pain VAS of genital ulcers, only subjects who had genital ulcers at baseline will be included.

The LOCF approach will be used to impute the missing assessment at Week 12 for the following endpoints: pain VAS of oral ulcers, pain VAS of genital ulcers, BD Current Activity Form Scores, BD QoL, and BSAS. The change from baseline at Week 12 (LOCF approach) will be compared between the placebo and the APR 30 BID group using ANCOVA model with change from baseline at Week 12 as the response variable, treatment, sex and region as factors and baseline value as a covariate. Within-group LS means, the associated SEs, and treatment differences in LS means, the associated SE, and associated 2-sided 95% CIs and 2-sided p-values will be derived from the model. A sensitivity analysis for change from baseline in the pain VAS of oral ulcers at Week 12 will be conducted using mixed-effects model for repeated measures (MMRM) with treatment, visit, treatment-by-visit interaction, sex and region as factors and baseline value as a covariate. An unstructured covariance matrix that is homogeneous across treatment groups is to be used.

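### The closest-to-target rule in SAP 5.4 usually drops an Early Termination ulcer count taken after a scheduled visit in the same window; the count then has no route into the primary analysis, and its role in LOCF is undefined

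*SAP*

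**What the plan says.** SAP 5.4 places all assessments into the Table 2 windows, which run from midpoint to midpoint between scheduled visits. If a window holds more than one assessment ("due to unscheduled visits or Early Termination visit"), then "the assessment within given visit window that is closest to the target Study Day will be used for the analysis", and a tie goes to the later one. The ET visit is thus expressly under the rule.

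SAP 4.2.5 builds AUC85 by trapezoids from one count and one date for each of Visits 2 to 9, with no ET term. SAP 10.2.2 imputes missing counts from treatment, sex, region and the counts at previous visits.

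On LOCF, SAP 4.2.5 states: "AUC using a last observation carried forward (LOCF) approach to impute missing assessments at Week 12 will be used as a sensitivity analysis". SAP 10.2.3 states: "The LOCF approach will be used to impute the missing assessment at Week 12 for the following endpoints: pain VAS of oral ulcers", and continues with genital ulcer pain, BDCAF, BD QoL and BSAS. SAP 4.2.5 also lists the PGA of skin lesions for LOCF. Neither section says whether the value carried forward is taken from the windowed record or from all assessments.

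Protocol 6.10 asks sites to collect data at withdrawal: "every effort should be made to complete as many safety and efficacy assessments as reasonably appropriate".

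**The concern.** The ET visit records a subject's state at departure. Protocol 12 and SAP 6 both list lack of efficacy as a reason for leaving, so some of these counts will be taken when ulcers have returned. A scheduled visit is meant to be on or near its target day, so an ET visit later in the same window will usually be further away and lose. Whether the count survives then depends on calendar spacing, not on its relevance. After a Week 6 visit on Day 43, an ET count on Day 50 is dropped and one on Day 51 is kept, because Day 51 opens the Week 8 window.

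In the primary analysis, an observed count is set aside and the following weeks are imputed from a history that ends before it. For LOCF, two programmers could reasonably derive different values for the AUC85 sensitivity analysis and for oral ulcer pain, the second endpoint in the testing sequence.

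**Working it through.** **The plan's own figure.** SAP 4.4 states: "A 2-sided t-test at a 0.05 significance level will have 90% power to detect a treatment difference of 66", "when the sample size in each group is 102, assuming a common standard deviation of 144". The standard error of the difference is 144 × √(2/102) = 20.16, and 66 / 20.16 = 3.27. Noncentral t power at 102 per group is 90.3%, so the figure reproduces. Nothing below changes it.

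**How often the rule drops the ET value.** Inputs are the Table 2 windows and the tolerances in Protocol Table 1 (±1 day at Weeks 1 and 2, ±3 days from Week 4). For each permitted scheduled day s and each later ET day e in the same window, ET is dropped if |e − target| > |s − target|.

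| Window | Day pairs | ET dropped | ET kept |
|---|---|---|---|
| Week 1 (Days 2–11) | 9 | 7 | 2 |
| Week 2 (Days 12–22) | 21 | 19 | 2 |
| Weeks 4, 6, 8, 10 (each) | 49 | 37 | 12 |
| Total | 226 | 174 (77%) | 52 (23%) |

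ET survives only when the scheduled visit was early. For example, with a scheduled visit on Day 26 and target Day 29, ET on Day 30 is closer and ET on Day 32 ties.

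**Share of ET days lost.** With scheduled visits on target, the lost days are 9–11, 16–22, 30–36, 44–50, 58–64 and 72–78: 3 + 5 × 7 = 38 of the 83 days from Day 2 to Day 84 (46%). With visits 1 to 3 days off target (1 day at Weeks 1 and 2), 24 to 32 of 83 are lost (29% to 39%). Leaving out Days 2–7 and the six target days from Day 8 to Day 71, the on-target share is 38 of 71 (54%).

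**How many subjects.** Protocol 1.3 reports that 100 of 111 Phase 2 subjects completed the double-blind phase and opted to continue, so at most 11/111 = 9.9% did not complete. Applied to 204, that is 20.2 subjects. If ET days are evenly spread, 20.2 × 24/83 = 5.8 to 20.2 × 38/83 = 9.3 lose their ET count; the 38/71 share gives 10.8.

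**One subject under LOCF (invented counts).** Counts are 3, 2, 1, 0, 0 on Days 1, 8, 15, 29 and 43, with ET on Day 49 showing 4 ulcers and later visits placed on target days.
- Observed part: 2.5×7 + 1.5×7 + 0.5×14 + 0×14 = 17.5 + 10.5 + 7 + 0 = 35.
- ET dropped, 0 carried to Day 85: AUC85 = 35.
- ET kept at its own date and carried forward: 35 + (0+4)/2 × 6 + 4 × 36 = 35 + 12 + 144 = 191.
- The shift is 156 ulcer-days with an ET count of 4, and half of that, 78, with a count of 2.

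**Arm means under LOCF.** If the ET value is used only from the next visit on, AUC85 moves by 73.5 ulcer-days per ulcer of difference when the last scheduled visit is Week 1, falling to 7 when it is Week 10. With 10.8 / 2 = 5.4 affected subjects per arm, the arm mean moves by 5.4 × 7 / 102 = 0.4 to 5.4 × 73.5 / 102 = 3.9 per ulcer of difference. If instead 9.3 / 2 = 4.6 per arm all shifted by 156, the mean would move by 4.6 × 156 / 102 = 7, against the standard error of about 20.

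**Primary analysis.** No corresponding figure can be given. The shift depends on how strongly later counts follow earlier ones in the imputation model, which the documents do not report.

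**The case against.** The strongest reply concerns LOCF. SAP 4.2.5 falls back on baseline only when there is no post-baseline value, and the one visit it excludes by name is the Observational Follow-up Visit. SAP 5.2 includes ET data in the efficacy period. On a plain reading, the last observation can be the ET value. This stands far enough that a reader should not infer that LOCF certainly ignores ET. It does not settle the matter. SAP 5.2 fixes the period, while SAP 5.4 selects the record to be used. The SAP also writes an explicit ET rule where it wants one: for the sustained-response endpoint in SAP 10.2.3 and for the safety end-of-treatment value in SAP 5.4. No such rule covers AUC85 or pain.

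Four other stronger readings are tempting and not supported.
- That ET is lost whenever it follows a scheduled visit in its window: 52 of the 226 day pairs keep it.
- That every LOCF endpoint is exposed: BDCAF, BD QoL and BSAS have no scheduled assessment between baseline and Week 12, so an earlier ET value has no competitor. The PGA is not scheduled at Weeks 6 or 10, so in the Day 49 example the ET PGA is kept.
- That a shift of 78 to 156 threatens the planned difference of 66: the first belongs to one subject, the second to arm means.
- That the rule favours one arm: it is prespecified and blind to treatment, an ET count may be lower than or equal to the previous one, and similar shifts in both arms would largely cancel. Differential bias is possible but not shown.

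**Conclusion.** The point holds for oral ulcer counts in the primary analysis. When an ET visit follows a scheduled visit in the same window, SAP 5.4 drops the ET count in most cases, and neither the AUC85 formula nor the imputation model gives it a way back. For LOCF (the AUC85 sensitivity analysis, oral and genital ulcer pain, and the PGA where one was scheduled in that window), the finding is an ambiguity: read with SAP 5.4, the value carried forward may not be the last observation.

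The size is modest: roughly 10 or fewer of 204 subjects and a small effect on arm means. This rests on four assumptions: Phase 2 non-completion applies here, ET days are evenly spread, every early leaver attends an ET visit, and day pairs stand in for frequencies that are not known. The 9.9% is an upper limit for Phase 2, since it also counts anyone who completed but chose not to continue. The reason to act is that the dropped values come from subjects who withdraw, where missing-data handling matters most. Label: cheap improvement.

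**What to change.** Keep the closest-to-target rule for by-visit tables. Before the Week 12 database lock, add to SAP 5.4, for subjects who discontinue before Week 12:

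1. LOCF carries forward the latest assessment by date, up to and including the ET visit and excluding the Observational Follow-up Visit.
2. For AUC85, the scheduled count and the ET count are both kept as trapezoid points at their own dates. In the imputation step, the ET count serves as that window's value when later visits are imputed.

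The ET count should not enter the imputation as a separate predictor variable. It exists only for subjects with no later counts, so its coefficient could not be estimated.

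The cost is one SAP paragraph, minor extra programming and an additional time point for a few subjects. No new data are needed, and sample size and power are unchanged.

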The mean oral ulcer counts in subjects randomized to the APR 30 BID group decreased sharply, reaching maximum reduction on Day 15 (first postbaseline assessment), and remained reduced for up to 24 weeks on treatment. In subjects randomized to the placebo group, the mean oral ulcer counts were consistently higher than in subjects randomized to the APR 30 BID group during the Treatment Phase. When the placebo subjects were transitioned to APR 30 BID in the Extension Phase, a reduction in mean oral ulcer counts was observed that was similar to those in the APR 30 BID-treated subjects. The oral ulcer counts increased in both treatment groups during the Observational Follow-up Phase when apremilast treatment was stopped.

Oral ulcer pain visual analog scale (VAS) scores in APR 30 BID- and placebo-treated subjects showed a pattern of change over time that was similar to that of oral ulcer counts. At Day 85, there was a more than 2-fold greater improvement (indicating decreased pain) in VAS scores from baseline in the APR 30 BID group compared with the placebo group (nominal  $p < 0.0001$ ). When the placebo subjects were transitioned to APR 30 BID in the Extension Phase, an improvement in oral ulcer pain VAS scores was observed that was similar to the APR 30 BID-

treated subjects. During the Observational Follow-up Phase, recurrence of pain was noted when apremilast treatment was stopped.

A small number of subjects had genital ulcers at baseline. Therefore, formal statistical comparisons between the APR 30 BID and placebo treatment groups were not done. However, a complete genital ulcer response (genital ulcer-free at Day 85) was achieved by all 10 (100%) subjects with baseline lesions in the APR 30 BID group versus 3 (50.0%) subjects with baseline lesions in the placebo group. Further, only 1 subject in the APR 30 BID group who did not have genital ulcers at baseline developed a single, new genital ulcer at Day 85, compared with 6 subjects in the placebo group.

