### **10.9. Other Topics**

## 11. ADVERSE EVENTS

### 11.1. Monitoring, Recording and Reporting of Adverse Events

An adverse event (AE) is any noxious, unintended, or untoward medical occurrence that may appear or worsen in a subject during the course of a study. It may be a new intercurrent illness, a worsening concomitant illness, an injury, or any concomitant impairment of the subject's health, including laboratory test values (as specified by the criteria in [Section 11.3](#)), regardless of etiology. Any worsening (ie, any clinically significant adverse change in the frequency or intensity of a pre-existing condition) should be considered an AE. A diagnosis or syndrome should be recorded on the AE page of the eCRF rather than the individual signs or symptoms of the diagnosis or syndrome.

Worsening of a subject's BD (any manifestation) should be considered as worsening of disease under study, and should not be captured as an AE, unless the event meets the definition of an SAE. Worsening of disease will be reported on the BD activity pages that lists each of the BD manifestations in the eCRF, and not captured in the AE eCRF. See [REDACTED] for more details.

Worsening of a subject's BD will be captured on the AE eCRF for subjects who continue in the optional Open-label Extension Phase after Week 64. Abuse, withdrawal, sensitivity or toxicity to an investigational product should be reported as an AE. Overdose, accidental or intentional, whether or not it is associated with an AE should be reported on the overdose eCRF (see [Section 8.3.2](#) for the definition of overdose). Any sequela of an accidental or intentional overdose of an investigational product should be reported as an AE on the AE eCRF. If the sequela of an overdose is an SAE, then the sequela must be reported on an SAE report form and on the AE eCRF. The overdose resulting in the SAE should be identified as the cause of the event on the SAE report form and in the eCRF but should not be reported as an SAE itself.

In the event of overdose, the subject should be monitored as appropriate and should receive supportive measures as necessary. There is no known specific antidote for apremilast overdose. Actual treatment should depend on the severity of the clinical situation and the judgment and experience of the treating physician.

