Subjects who qualify for enrollment will be randomized 1:1 to receive APR 30 BID or identically-appearing placebo tablets BID for the 12-week Placebo-controlled Treatment Phase. To mitigate potential gastrointestinal (GI) side effects dose titration will be implemented in the first week of this study. For dose titration, 10 mg, 20 mg and 30 mg apremilast tablets, or identically appearing placebo tablets, will be dispensed in dose titration cards at Week 0.

Active Treatment Phase

All subjects who complete the Placebo-controlled Treatment Phase will be eligible to enter the Active Treatment Phase. Subjects initially randomized to placebo will transition to APR 30 BID, while subjects initially randomized to APR 30 BID will continue on the same treatment during the 52-week Active Treatment Phase. To maintain the blind regarding the initial treatment assignment, all subjects will receive dose titration cards at Visit 9 (Week 12). Although only subjects initially randomized to placebo will be dose titrated during their first week of the Active Treatment Phase, all subjects entering the Active Treatment Phase will receive identically-appearing titration/treatment cards.

Posttreatment Observational Follow-up Phase

Subjects who discontinue at any time from the study for any reason are to enter the 4-week Posttreatment Observational Follow-up Phase to monitor changes in disease activity or safety parameters.

Optional Open-label Extension Phase

Subjects from German sites who complete Visit 14 of the 52-week Active Treatment Phase will have an opportunity to continue to receive APR 30 BID in an optional Open-label Extension Phase.

End of Trial

The End of Trial is defined as either the date of the last visit of the last subject to complete the study, or the date of receipt of the last data point from the last subject that is required for primary, secondary analysis, as pre-specified in the protocol and/or the SAP, whichever is the later date.

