10.3. Efficacy Evaluation for the Active Treatment Phase in the Final Analysis

All subjects entering into the Active Treatment Phase of the study will be included in the analysis. Descriptive summaries for the endpoints as listed below will be performed at each applicable study visits based on the observed data by treatment sequence.

- Complete response [REDACTED] rate for oral ulcers
- Complete response rate for genital ulcers for subjects who had genital ulcers at baseline
- Number of oral ulcers
- Number of genital ulcers
- Change from baseline in the pain of oral ulcers as measured by VAS
- Change from baseline in the pain of genital ulcers, as measured by VAS in subjects who had genital ulcers at baseline
- Change from baseline in disease activity as measured by BD Current Activity scores (BD Current Activity Form)
- Change from baseline in the BD QoL score
- Change from baseline in Behçet's Syndrome Activity Score (BSAS)
- Change from baseline in the total score of the Static Physician's Global Assessment (PGA) of skin lesions (acne-like lesions, folliculitis and erythema nodosum) of BD in subjects who had BD skin lesions at baseline

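### Off-drug efficacy values from the Observational Follow-up Visit have no analysis time point and no visible summary, and some early discontinuers' values would be labelled as treatment-phase weeks

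*SAP*

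**What the plan says.** **Why the visit exists.** Protocol 1.3 reports from Phase 2: "The oral ulcer counts increased in both treatment groups during the Observational Follow-up Phase when apremilast treatment was stopped". It adds that ulcer pain recurred. SAP 4.1 says that subjects who discontinue "are to enter the 4-week Posttreatment Observational Follow-up Phase to monitor changes in disease activity or safety parameters".

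**What is collected.** SAP 4.2.5 states: "The number of oral ulcers and genital ulcers will be counted at each study visit, at ET and Observational Follow-up visits". Protocol Table 1 also marks both pain VAS scales, BDCAF, BD QoL, BSAS and the skin PGA at Visit 15 (Week 68).

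**How values reach a table.**
- SAP 5.2 includes the Observational Follow-up Visit in the efficacy periods.
- SAP 5.4 says "all assessments will be assigned to analysis visits according to a visit window schema". Neither Table 2 nor Table 3 has a Follow-up row.
- The Week 64 window closes "1 day prior to date of Observational Follow-up Visit if Observational Follow-up Visit performed". The Week 12 window closes the day before the visit for subjects who stop before Visit 9. The remaining post-baseline windows in Table 2 carry no follow-up exclusion.
- SAP 10.3, on the Active Treatment Phase, says: "Descriptive summaries for the endpoints as listed below will be performed at each applicable study visits based on the observed data by treatment sequence".

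**Worsening as an event.** Protocol 11.1 says: "Worsening of a subject's BD (any manifestation) should be considered as worsening of disease under study, and should not be captured as an AE", with an exception for serious events. Such worsening goes on a BD activity page of the eCRF. Protocol 6.6.1 states the same rule only for the first 64 weeks.

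**The concern.** Return of disease after stopping is an off-drug effect that the sponsor has already observed, and the SAP gives monitoring of disease activity as a purpose of the follow-up phase. The data are collected, but the visible rules do not say where they go. There are two consequences. Completers' off-drug values may be summarised nowhere. Some early discontinuers' off-drug values may appear in by-visit tables as if they belonged to a treatment-phase week. In either case a reader of the results could not tell how far disease returns once apremilast is stopped. The event route does not clearly fill the gap, because non-serious worsening is kept off the AE page and no visible SAP section summarises post-baseline data from the BD activity page.

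**Working it through.** The plan gives no figure on this point, so there is none to reproduce. The check places the follow-up visit in the Table 2 windows.

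**Inputs.** Window limits are from SAP Table 2. The follow-up visit is 4 weeks after last dose, with a tolerance of 7 days either way (protocol 6.9). I assume that Visit 9 and the first active-phase dose fall on Day 85, so the Week 16 window opens on Day 86.

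**Formula.** Follow-up day = last-dose day + 28.

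| Last dose (study day) | Follow-up day | Table 2 window |
|---|---|---|
| 1–8 | 29–36 | Week 4 (23–36) |
| 9–22 | 37–50 | Week 6 (37–50) |
| 23–36 | 51–64 | Week 8 (51–64) |
| 37–50 | 65–78 | Week 10 (65–78) |
| 51–84 | 79–112 | none: Week 12 closes the day before the visit |
| 85–127 | 113–155 | Week 16 (86–155) |
| 128–211 | 156–239 | Week 28 (156–239) |
| 212–295 | 240–323 | Week 40 (240–323) |
| 296–379 | 324–407 | Week 52 (324–407) |
| 380–449 | 408–477 | none: Week 64 closes the day before the visit |

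The last row includes completers (last dose about Day 449).

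**Extent.** In the placebo-controlled phase, 8 + 14 + 14 + 14 = 50 of the 84 possible last-dose days put the follow-up value in a treatment-phase window. In the active phase it is 43 + 84 + 84 + 84 = 295 of 365 (Days 85 to 449). These are counts of days, not of subjects.

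**Tolerance.** With the visit 21 to 35 days after last dose, the upper limits move to 78 − 35 = 43 through 78 − 21 = 57 in the first phase, and 407 − 35 = 372 through 407 − 21 = 386 in the second. The pattern does not change.

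**Would the value be used?** SAP 5.4 takes the assessment nearest the target day.
- Last dose on Day 30: follow-up is on Day 58, one day from the Week 8 target of 57. An Early Termination Visit near Day 30 lies in the Week 4 window, so the off-drug value would be the only one in Week 8.
- Last dose on Day 170, with an Early Termination Visit that day: follow-up is on Day 198, one day from the Week 28 target of 197. The termination value is 27 days away, so the off-drug value would be chosen over it.

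**Events.** Completers' follow-up is at Week 68. Section 6.6.1 limits its rule to the first 64 weeks, while 11.1 has no such limit outside the open-label extension. For Weeks 64 to 68 the two sections differ.

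**What a table could show.** The documents do not give attendance at the visit. If 120 to 180 of the 204 subjects attend (assumption), the 95% half-width for a proportion near 50% is 1.96 × √(0.25/n): 8.9 points at 120, 8.0 at 150 and 7.3 at 180. This is the precision of a possible descriptive summary, not a loss in any planned analysis.

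**The case against.** The case against is substantial.

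- **Reporting is not ruled out.** SAP 5.2 includes the follow-up visit in the efficacy period, SAP 2 plans Week 68 efficacy analyses, and 10.3 covers every applicable visit. This stands. A reader might infer that disease return would certainly go unreported, but the documents do not support that. What remains is that 5.2 includes a visit which 5.4 does not label, so reporting is unspecified.
- **The closing rule for Week 64 is sound.** It keeps off-drug values out of an on-treatment week. That is correct. The gap is that the values get no time point of their own and that most other windows lack the same stop.
- **AE capture is not closed.** Serious worsening is recorded as an AE, 6.6.1 limits its rule to 64 weeks, the BD activity page exists for this purpose, and SAP 11.2.13 summarises TEAEs up to 28 days after last dose. A reader might infer a complete bar, but the text does not say so.
- **Phase 2 did not report counts above baseline after stopping.** It reported an increase and a recurrence of pain. Reading this as a rebound beyond baseline goes further than the source.
- **No visible objective or endpoint concerns withdrawal, and parts of the plan are not shown.** SAP 4.2.1.3, 10.2.4 and Section 13 are not visible, 10.3 carries a redaction, and the protocol's exploratory endpoints are blacked out. A follow-up analysis there cannot be excluded.

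A reader might also infer that the primary AUC is distorted, because Week 4 to 10 counts enter it. The documents do not establish this. They give no number of early discontinuers, and the LOCF rules in SAP 4.2.5 set the follow-up value aside when deciding whether a subject has a post-baseline assessment, which suggests that it was not meant to count.

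**Conclusion.** The point holds as a gap and an inconsistency in the SAP. Follow-up efficacy data are inside the analysis period (5.2) but have no time point (5.4) and no named summary in any readable section. Read literally, completers' off-drug values fall in no window. Values from subjects with a last dose on Days 1 to 50 or 85 to 379 fall in treatment-phase windows. Return of disease after stopping may therefore not be summarised, or may be mislabelled as on-treatment.

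This rests on a follow-up visit at about last dose + 28 days, on Visit 9 at Day 85, and on the absence of a relevant analysis in the sections not shown. How many subjects are affected cannot be derived from the documents. By contrast, the SAP does name summaries for follow-up concomitant medications (8.5) and for TEAEs after last dose (11.2.13), so the gap is specific to disease activity. It should be corrected.

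**What to change.** 1. **SAP 5.4.** Add an Observational Follow-up row to Table 2, about 4 weeks after last dose, and exclude follow-up values from all other windows. Word it consistently with 5.2. The Week 4 to 10 windows are used in the Week 12 analyses, so this is best settled before that database lock.
2. **SAP 10.3.** Add a descriptive table by treatment sequence, with completers and early terminators shown separately, for oral ulcer count, oral ulcer pain VAS, BSAS and BDCAF at follow-up. Give the change from the last on-treatment value, the change from baseline, and the proportion with an oral ulcer count above baseline. Also summarise the post-baseline entries on the BD activity page.
3. **Protocol 6.6.1 and 11.1.** Reconcile the two sections on how worsening of BD is recorded between Weeks 64 and 68. This review does not say which rule is right.

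The cost is SAP wording and one or two descriptive tables, plus the reconciliation of two protocol sections. No new data or visits are needed.
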